#### 11.6. Derived and transformed data

##### 11.6.1. Demography

For a given subject and a given demographic variable, missing measurements will not be replaced.

##### 11.6.2. Safety

For a given subject and the analysis of solicited AEs during the 7-day follow-up period after vaccination, missing or non-evaluable measurements will not be replaced.

Therefore, the analysis of the solicited symptoms based on the ES will include only vaccinated subjects with documented safety data (i.e., symptom screen completed).

For analysis of unsolicited AEs, SAEs and for the analysis of concomitant medications, all vaccinated subjects will be considered. Subjects who did not report an event or concomitant medication will be considered as subjects without the event or the concomitant medication respectively.

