**10.2.1. Subject withdrawal from the study**

From an analysis perspective, a ‘withdrawal’ from the study refers to any subject who did not come back for the concluding visit foreseen in the protocol.

All data collected until the date of withdrawal/last contact of the subject will be used for the analysis.

A subject is considered a ‘withdrawal’ from the study when no study procedure has occurred, no follow-up has been performed and no further information has been collected for this subject from the date of withdrawal/last contact.

Investigators will make an attempt (e.g., three telephone calls and a certified letter to the last known address) to contact those subjects who do not return for scheduled visits or follow-up.

Information relative to the withdrawal will be documented in the eCRF. The investigator will document whether the decision to withdraw a subject from the study was made by the subject's parent(s)/LAR(s), or by the investigator, as well as which of the following possible reasons was responsible for withdrawal:

- Serious adverse event.
- Unsolicited non-serious adverse event.
- Solicited adverse event
- Protocol violation (specify).
- Consent withdrawal, not due to an adverse event\*.
- Moved from the study area.
- Lost to follow-up.
- Other (specify).

\*In case a subject is withdrawn from the study because he/she/the subject's parent(s)/LAR(s) has withdrawn consent, the investigator will document the reason for withdrawal of consent, if specified by the subject/subject's parent(s)/LAR(s), in the eCRF.

Subjects who are withdrawn from the study because of SAEs/AEs must be clearly distinguished from subjects who are withdrawn for other reasons. Investigators will follow subjects who are withdrawn from the study as result of a SAE/AE until resolution of the event (see Section 9.5.1.1).

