## 11.2. Secondary endpoints

- Occurrence of RSV-RTI, RSV-LRTI, severe RSV-LRTI and very severe RSV-LRTI (according to standardized case definitions) as from first vaccination (Day 1) up to the end of the first RSV transmission season.
- Occurrence of RSV-RTI, RSV-LRTI, severe RSV-LRTI and very severe RSV-LRTI (according to standardized case definitions) as from first vaccination (Day 1) up to the end of the second RSV transmission season.
- Occurrence of SAEs from first vaccination (Day 1) up to the end of the second RSV transmission season.
- Occurrence of RSV-LRTI (AE of special interest) as from first vaccination (Day 1) up to the end of the first RSV transmission season, and up to the end of the second RSV transmission season.
- Occurrence of very severe RSV-LRTI (according to standardized case definitions) among RSV infected infants with a negative RSV exposure status (at screening based on in-stream baseline serological testing) from first vaccination (Day 1) up to the end of the first RSV transmission season.
- Humoral response to the investigational RSV vaccine, pre-vaccination (Screening), post-Dose 1 (Day 31) and post-Dose 2 (Day 61 and at the end of the first RSV transmission season):
  - Neutralizing antibody titers against RSV-A.
  - RSV F antibody concentrations.

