If a maximum of 1 out of 5 infections in infants receiving ChAd-155 RSV vaccine progress to very severe RSV-LRTI, then it can be concluded with 95% confidence that the expected progression rate of infection is less than the effect reported in previous FI-RSV trials; if a minimum of 3 out of 5 infections progress to very severe RSV-LRTI then it can be concluded with 95% confidence that the expected progression rate of infection is more than the 10% observed in natural history of infection. The above power analysis is based on the procedure of inequality of one proportion in PASS 12.

With 50 subjects in each RSV vaccine group, the probability of observing at least one SAE would be about 92% if the true incidence rate of SAE is 5%. For estimating the proportion of subjects with AEs, the maximum width of exact 95% confidence interval (CI) would be under 30%, and it could be as large as 35% if attrition rate is 30%.

**Figure 6** illustrates the precision on the estimate for the proportion of subjects with AEs following vaccination with each RSV formulation based on the number of subjects with AEs observed from 50 subjects.

**Figure 6    Exact 95% confidence interval on the proportion of subjects with adverse events following vaccination based on 50 enrolled subjects**

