The percentage of subjects with RSV-LRTI (AE of specific interest) from Dose 1 up to end of the first RSV transmission season and from Dose 1 up to end of second RSV season will be tabulated according to associated Preferred Term code presented in the SAP.

The percentage of subjects with SAE within 30 days (Day 1-30) after each vaccine dose with its exact 95% CI will be tabulated and by MedDRA preferred term. Similar tables will be generated for SAEs from Dose 1 to end of first RSV season and from Dose 1 to end of the second RSV season.

SAEs reported throughout the study and AE of special interest will be described in detail.

The percentage of subjects using concomitant medication (any medication, any antipyretic and any antipyretic taken prophylactically, respectively) during the 7-day follow-up period (Day 1-7) and during the 30-day follow-up period (Day 1-30) will be

summarized by the pooled RSV vaccine and pooled comparator groups after each vaccine dose and overall.

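### Infants who leave without a reported SAE stay in the denominator as event-free, so the SAE percentages to the end of the first and second RSV seasons are biased downward

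*Protocol*

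**What the plan says.** Section 11.6.2 sets the analysis population: "For analysis of unsolicited AEs, SAEs and for the analysis of concomitant medications, all vaccinated subjects will be considered". The next sentence covers infants with nothing reported: "Subjects who did not report an event or concomitant medication will be considered as subjects without the event or the concomitant medication respectively". Neither sentence makes this conditional on the infant having been followed to the end of the period.

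Section 11.2 lists a long-term secondary endpoint: "Occurrence of SAEs from first vaccination (Day 1) up to the end of the second RSV transmission season". Section 11.8.1 begins with the short window, "The percentage of subjects with SAE within 30 days (Day 1-30) after each vaccine dose with its exact 95% CI will be tabulated", and then extends it: "Similar tables will be generated for SAEs from Dose 1 to end of first RSV season", with the same again to the end of the second season. For the adverse event of special interest it plans "The percentage of subjects with RSV-LRTI (AE of specific interest) from Dose 1 up to end of the first RSV transmission season" and likewise to the end of the second season.

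On leavers, Section 10.2 states that withdrawals are not replaced. Section 10.2.1 defines a withdrawal as an infant on whom no further information is gathered, and says: "All data collected until the date of withdrawal/last contact of the subject will be used for the analysis". Section 3 gives the study duration as about 24 months. No censoring, person-time or completer denominator is stated for SAEs.

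**The concern.** Treating no report as no event is reasonable over a 30-day window, when almost every infant is still under observation. Over two RSV seasons it is not the same thing. An infant who leaves in month 3 with nothing reported contributes a full period of apparent safety, most of it unobserved. The resulting percentage estimates the share with an SAE reported while in the study. It reads as the risk to the end of the second season, and it falls below that risk whenever anyone leaves early.

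The direction matters because long-term safety is a secondary objective of a first study in infants likely to be unexposed to RSV. An error toward fewer events is the less welcome one.

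**Working it through.** **Inputs**
- From Section 11.4: 50 infants per RSV group, a 5% SAE rate as the worked example, and 30% as a hypothetical attrition figure.
- Assumed: a constant event rate over follow-up; dropout unrelated to risk; leavers spread evenly over follow-up, or all leaving immediately after dosing as the worst case. The protocol gives neither an expected dropout nor dropout by arm, so ranges are shown.

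**The plan's own figures first**
- Chance of at least one SAE: 1 − 0.95^50 = 92.3%, against the stated figure of about 92%.
- Widest exact 95% interval: 28.9% at n = 50, against the stated limit of under 30%. At n = 50 × 0.7 = 35 it is 34.6%. This matches the statement that "it could be as large as 35% if attrition rate is 30" per cent.

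All of these reproduce. The last one takes lost infants out of the denominator, whereas Section 11.6.2 leaves them in for unsolicited AEs and SAEs. That is not a firm contradiction, because the solicited-event analysis does use only infants with documented data.

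**Size of the bias**

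Let p be the risk over full follow-up, d the share who leave, and L = −ln(1 − p).
- Expected percentage under the rule: (1 − d)·p + d·E, where E is a leaver's chance of an event before leaving.
- Even dropout: E = 1 − p/L. Immediate dropout: E = 0.
- For p = 5%: L = 0.05129 and E = 1 − 0.05/0.05129 = 2.52%.

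| Dropout | Even | Immediate |
|---|---|---|
| 10% | 0.9 × 5 + 0.1 × 2.52 = 4.75% | 4.5% |
| 20% | 0.8 × 5 + 0.2 × 2.52 = 4.50% | 4.0% |
| 30% | 0.7 × 5 + 0.3 × 2.52 = 4.26% | 3.5% |

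At 30% dropout the shortfall is 0.74 points with even dropout (about 15% relative) and at most 1.5 points (30% relative). Per 50 infants that is 0.37 and 0.75 of an infant. A true 10% reads 8.53% at 30% even dropout. Over full follow-up, the chance of recording at least one SAE at a true 5% falls from 92.3% to 88.6% (even) or 83.2% (immediate).

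**Effect on the ratio of two arms with no true difference (p = 5%)**
- Equal dropout: 1.00.
- 30% against 10%: 4.26/4.75 = 0.90 (even), or 3.5/4.5 = 0.78 (immediate).

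The split of 30% against 10% is purely illustrative.

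**The case against.** The best defence is that the percentage of vaccinated infants with a reported SAE is a clearly stated descriptive summary, and that the bias is small beside the sampling error. At 5 events in 50 the exact 95% interval runs from roughly 3% to 22%. Section 11.7 already tabulates withdrawals by group and reason, and Section 11.8.1 promises a detailed description of SAEs. Exposure-adjusted displays are often left to the analysis plan. The point about size stands. The last point does not dispose of the matter, because the protocol itself fixes how non-reporters are counted and what is tabulated over the long periods. A table of withdrawal reasons also does not give follow-up time.

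A reader might infer more than the documents support:

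- **Every infant who withdraws is counted as event-free.** No. Section 10.2.1 keeps data up to withdrawal, so an SAE reported before leaving is counted, including one that caused the withdrawal. Only infants with none reported are affected.
- **The planned arm comparison is distorted.** The long-term tables belong to the within-group assessment. The between-group safety comparison in Section 11.8.2 uses 7-day windows, where dropout hardly matters, and Section 11.11 calls comparisons exploratory. Reading the long-term tables side by side would mislead only if dropout differed by arm, and the protocol gives no figure for that.
- **The test for enhanced RSV disease is biased.** That analysis (Sections 11.4, 11.10 and 11.11) concerns progression to very severe RSV-LRTI among RSV-infected infants and does not use this rule. Holding rule 2d is a count.
- **Section 11.6.2 governs the special-interest RSV-LRTI table.** It does not name events of special interest. The reason to include that table in the fix is that Section 11.8.1 gives it as a simple percentage over the same long periods, with no censoring stated.
- **Section 11.10 treats the same leaver differently.** It speaks of incidence rates but never defines them by person-time. Its rate among infected infants is compared with 80% in Section 11.11, so there it is a proportion. No inconsistency is shown.

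**Conclusion.** The concern holds for the within-group SAE percentages to the end of the first and second RSV seasons. Followed as written, the plan biases them downward whenever infants leave early. At the protocol's 5% example the shortfall is about 0.25 points at 10% even dropout and 0.74 points at 30%, with 1.5 points as the worst case at 30%. These sizes rest on a constant event rate, which is a simplification for seasonal disease, on dropout unrelated to risk, and on assumed dropout levels. The direction of the bias does not depend on the exact values.

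The 30-day tables and the 7-day comparison are essentially untouched. This is a worthwhile, inexpensive improvement to a secondary safety display. It does not threaten the trial's main conclusions.

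**What to change.** In Section 11.6.2, keep the rule that no report means no event for the 30-day windows, and keep the Exposed Set percentage for the longer periods as a description of what was reported.

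In Section 11.8.1, for SAEs from Dose 1 to the end of the first and of the second season, and for the special-interest RSV-LRTI percentages over the same periods, add one of:
- infants with an event per unit of person-time; or
- a Kaplan-Meier cumulative percentage censored at last contact.

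Show follow-up time by pooled group beside it. If dropout is unrelated to risk and the event rate is constant, either measure removes the bias; the Kaplan-Meier percentage does not need the constant rate.

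The cost is a few table columns and slightly less favourable reported rates. No new data are needed, since withdrawal information and surveillance contacts are already recorded in the eCRF (Sections 9.2 and 10.2.1).

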### 11.6.3. Immunogenicity

Any missing or non-evaluable immunogenicity measurement will not be replaced:

- For the within-group assessment, the descriptive analysis performed for each assay at each timepoint will exclude subjects with a missing or non-evaluable measurement. Kinetics will be plotted on subjects with results available at all timepoints.

The geometric mean titers/concentrations (GMTs/GMCs) will be computed by taking the anti-logarithm of the arithmetic mean of the log10 transformed titers/concentrations.

A seronegative subject will be defined as a subject whose antibody titer/concentration is below the cut-off value of the assay. A seropositive subject is a subject whose antibody titer/concentration is greater than or equal to the cut-off value of the assay.

Determination of a negative RSV exposure status in infants at 6 to 7 months of age will be based on RSV A and/or B neutralizing antibody titers present in serum at screening (before vaccination with the RSV vaccine) based on in-stream baseline serological testing. At birth, newborns do show positive for neutralizing antibodies due to maternal transfer during gestation. The titer of these antibodies declines over time. At the age of 6 to 7 months a cut-off can be defined below which infants are considered to have a negative RSV exposure status. Infants that show neutralizing antibody titers above this cut-off are suspected to have experienced a recent RSV infection. This cut-off will thus allow the discrimination between a negative RSV exposure status versus RSV infected infants before start of vaccination.

The description of the handling of data below the lower limit of quantification for GMC calculation and fold increase will be described in the statistical analysis plan.

### 11.6.4. RTI and LRTI

For the analysis of RTI and LRTI, all cases will be definitively classified as either RSV-RTI, RSV-LRTI, severe RSV-LRTI or very severe RSV-LRTI according to the case definitions presented in [Table 6](#), and the association to RSV infection will be assessed by quantitative PCR as primary analysis.

All confirmed LRTI will also be investigated for a panel of respiratory viruses (multiplex PCR; refer to [Table 11](#)), as a supplementary analysis of the occurrence of RSV-LRTI diagnosed upon the multiplex PCR.

For the analysis of RTI episode, a new RTI episode will be defined as any occurrence of cough, runny nose, blocked nose with an interval of at least 7 symptom free days since the last episode of RTI that was diagnosed. *For the analysis of LRTI episode, a new LRTI episode will be defined as a history of cough or difficulty breathing and blood oxygen saturation < 95%, or respiratory rate increase and confirmed RSV infection with an interval of at least 7 symptom free days since the last episode of LRTI that was diagnosed (Amended 1 August 2019).*

## 11.7. Analysis of demographics

The analysis of demographics will be performed on the ES and on the PPS cohort for immunogenicity for each RSV + comparator vaccine group and each active control comparator group and also for the pooled RSV vaccine and pooled comparator groups.

Demographic characteristics (age at vaccination in months, sex, country and race and vital signs), cohort description will be summarized by group using descriptive statistics:

- Frequency tables will be generated for categorical variables such as race.
- Mean, median, standard error and range will be provided for continuous data such as age.

The distribution of subjects will be tabulated as a whole and per group.

Withdrawal status will be summarized by group using descriptive statistics:

- The number of subjects enrolled into the study as well as the number of subjects excluded from PP analyses will be tabulated.
- The numbers of withdrawn subjects will be tabulated according to the reason for withdrawal.

## 11.8. Analysis of safety

### 11.8.1. Within groups assessment

The safety will be descriptively summarized based on the ES. The analysis of local AEs, general AEs and fever will be reported for each RSV + comparator vaccine group and each active control comparator group and also for the pooled RSV vaccine and pooled comparator groups. For the analysis of SAEs and AE of specific interest, the analysis will be performed only on the pooled RSV and pooled comparator groups.

The percentage of subjects with at least one local AE (solicited and unsolicited), with at least one general AE (solicited and unsolicited) and with any AE during the 7-day or 30-day follow-up period will be tabulated with exact 95% confidence interval (CI) after each vaccine dose and overall. The percentage of doses followed by at least one local AE (solicited and unsolicited), by at least one general AE (solicited and unsolicited) and by any AE during the 7-day or 30-day follow-up period will be tabulated, overall vaccination course, with exact 95% CI. The same computations will be done for Grade 3 AEs, for any AEs considered related to vaccination for any Grade 3 AEs considered related to vaccination and AEs resulting in a medically attended visit.

The percentage of subjects reporting each individual solicited local AE (any grade, Grade 2, Grade 3, resulting in a medically attended visit) and solicited general AE (any grade, Grade 2, Grade 3, any related, Grade 2 related, Grade 3 related, resulting in medically attended visit) during the 7-day follow-up period (Day 1-7) will be tabulated for each RSV + comparator vaccine group and each active control comparator group and also for the pooled RSV vaccine and pooled comparator groups after each vaccine dose and

overall. Similarly, the percentage of doses followed by each individual solicited local and general AE and their sub-categories, will be tabulated, overall vaccination course, with exact 95% CI.

For fever, the number and percentage of subjects reporting fever by half degree (°C) cumulative increments during the 7-day follow-up period (Day 1-7) will be tabulated for each RSV + comparator vaccine group and each active control comparator group and also for the pooled RSV vaccine and pooled comparator groups after each vaccine dose and overall. Similar tabulations will be performed for any fever with a causal relationship to vaccination, Grade 3 ( $> 40.0^{\circ}\text{C}$ ) causally related fever and for any fever resulting in a medically attended visit. In addition, the prevalence of any and Grade 3 fever will be presented graphically over time after vaccination.

For clinical safety laboratory parameters: a listing of laboratory value outside the normal range for the unscheduled visits will be provided as per the toxicity scale. The maximum grading during the study will be tabulated (Refer to [APPENDIX C](#)) Laboratory values will be classified according to toxicity criteria. Laboratory values that are outside the normal range will also be flagged in the data listings, along with corresponding normal ranges and assessment of clinical significance (**Amended 1 August 2019**).

The percentage of subjects with unsolicited AEs within 30 days (Day 1-30) after each vaccine dose (overall doses) with its exact 95% CI will be tabulated RSV + comparator vaccine group and each active control comparator group and also for the pooled RSV vaccine and pooled comparator groups and by MedDRA preferred term. Similar tabulation will be done for Grade 3 unsolicited AEs, for any causally related unsolicited AEs, for Grade 3 causally related unsolicited AEs and for unsolicited AEs resulting in a medically attended visit. The verbatim reports of unsolicited AEs will be reviewed by a physician and the signs and AEs will be coded according to the MedDRA Dictionary for Adverse Reaction Terminology. Every verbatim term will be matched with the appropriate Preferred Term. The percentage of subject with episode of spontaneous or excessive bleeding (AE of specific interest), during a 30-day follow-up period after each vaccination will be tabulated according to associated Preferred Term code (to be identified in the Statistical Analysis Plan [SAP]).

The percentage of subjects with RSV-LRTI (AE of specific interest) from Dose 1 up to end of the first RSV transmission season and from Dose 1 up to end of second RSV season will be tabulated according to associated Preferred Term code presented in the SAP.

The percentage of subjects with SAE within 30 days (Day 1-30) after each vaccine dose with its exact 95% CI will be tabulated and by MedDRA preferred term. Similar tables will be generated for SAEs from Dose 1 to end of first RSV season and from Dose 1 to end of the second RSV season.

SAEs reported throughout the study and AE of special interest will be described in detail.

The percentage of subjects using concomitant medication (any medication, any antipyretic and any antipyretic taken prophylactically, respectively) during the 7-day follow-up period (Day 1-7) and during the 30-day follow-up period (Day 1-30) will be

summarized by the pooled RSV vaccine and pooled comparator groups after each vaccine dose and overall.

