    - In the 1 Dose (1D) groups, a single lower dose of 1.5x10^10 vp will be administered IM at Day 1 (Visit 1). Formulation buffer will be administered in the 1D groups at Day 31 (Visit 3). In the 2 Dose (2D) groups, two doses of 5x10^10 vp will be administered IM according to a 0, 1-month schedule, (i.e., at Day 1 [Visit 1] and Day 31 [Visit 3]) (see [Figure 1](#) and [Table 2](#)). Dose 1 will be administered before the first RSV season and the second dose will be given one month after the first dose (RSV seasons will be determined for each country based on local epidemiological data and documented in the Study Procedures Manual [SPM]. The RSV season is defined as the period of the year when 70% of the RSV cases have occurred in previous years. For the calculation, where available, data from up to the ten previous years should be applied. If the data permit calculation of the actual date of the beginning of the season, rather than approximation to the nearest month, this is desirable..

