**6.6.15. Recording of AEs, AEs of special interest and SAEs**

- Refer to Section 9.3 for procedures for the investigator to record AEs, AEs of special interest (RSV-LRTI) and SAEs. Refer to Section 9.4 for guidelines and how to report AEs of special interest and SAE reports to GSK Biologicals.
- The subjects' parent(s)/LAR(s) will be instructed to contact the investigator immediately should the subjects manifest any signs or symptoms they perceive as serious.
- Subjects' parent(s)/LAR(s) will be instructed to contact the investigator/study staff if their child presents symptoms of spontaneous bleeding or easy bruising or if their child develops a rash, within 30 days after either vaccination (Visit 1 and Visit 3), in order to detect any thrombocytopenic petechiae or purpura after each vaccination from Visit 1 [Day 1] to Visit 5 Day 61.
- At each vaccination visit of the RSV investigational vaccine (Visit 1 [Day 1] and Visit 3 [Day 31]), a diary card will be provided to the subject's parent(s)/LAR(s). The subject's parent(s)/LAR(s) will be instructed to measure and record the rectal body temperature (preferred route), any solicited local/general AEs, any unsolicited AEs, and concomitant medications/products/vaccinations on the day of vaccination and 6 subsequent days. The subject's parent(s)/LAR(s) will be instructed to return the completed diary card to the investigator at Visit 2 (Day 8) and Visit 4 (Day 38).

The subject's parent(s)/LAR(s) will record on the same diary card any unsolicited AEs and concomitant medications/products/vaccinations from 7 to 29 days after each vaccination. The subject's parent(s)/LAR(s) will be instructed to return the completed diary card to the investigator at Visit 3 (Day 31) and Visit 5 (Day 61).

The investigator will collect and verify completed diary cards during discussion with the subject's parent(s)/LAR(s) on Visit 2 (Day 8), Visit 3 (Day 31), Visit 4 (Day 38), and Visit 5 (Day 61). The investigator will transcribe the collected information into the eCRF in English.

Any unreturned diary cards will be sought from the subject's parent(s)/LAR(s) through telephone call(s) or any other convenient procedure.

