Synflorix	Synflorix 10Pn-PD-DiT	PS1=1µg PD; PS4=3µg PD; PS5=1µg PD; PS6B=1µg PD; PS7F=1µg PD; PS9V=1µg PD; PS14=1µg PD; PS18C=3µg TT; PS19F=3µg DT; PS23F=1µg PD; PD=9-16µg; DT=3-6µg; TT=5-10µg; AlPO 4 =500µg Al3+	Turbid white suspension	0.5 ml	3

† Clear, colorless solution free from visible particles.

‡ The number of Formulation buffer doses depends on the study arm and study country (see [Table 2](#)).

§ MenACWY-TT, a white powder or cake, is resuspended with a NaCl solution, to make Nimenrix.

\* MenA lyo, a lyophilized component, is resuspended with MenCWY liquid, to make Menveo.

\* Formulation buffer will be administered, when neither RSV vaccine nor comparator is scheduled, at the vaccination visits (see [Figure 1](#), [Table 2](#) and [Table 16](#)).

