## **11. STATISTICAL METHODS**

### **11.1. Primary endpoints**

- Occurrence of adverse events (AEs) from first vaccination (Day 1) up to Day 61.
  - Occurrence of each solicited local and general AE, during a 7-day follow-up period after each vaccination (i.e., the day of vaccination and 6 subsequent days).
  - Occurrence of any unsolicited AE, during a 30-day follow-up period after each vaccination (i.e., the day of vaccination and 29 subsequent days).
  - Occurrence of any serious adverse event (SAE) from Day 1 up to Day 61.
  - Occurrence of episode of spontaneous or excessive bleeding (AE of special interest), during a 30-day follow-up period after each vaccination.

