#### 11.5.4. Pooled groups in the study

All subjects in the single dose (1D,  $1.5 \times 10^{10}$  vp) RSV + comparator vaccine groups will be pooled together as the pooled 1D RSV group, similarly, all subjects in the two dose (2D,  $5 \times 10^{10}$  vp) RSV + comparator vaccine groups will be pooled together as the pooled 2D RSV group, and all subjects in the comparator/Placebo control vaccine alone groups will be pooled together as the pooled comparator group ([Table 25](#)).

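### The course-level per-dose AE percentages in Section 11.8.1 mix buffer with vaccine injections in 1D but not in 2D, and their exact CIs ignore that each infant contributes two injections

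*Protocol*

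**What the plan says.** Section 11.8.1 plans two kinds of AE percentage. The first counts infants and "will be tabulated with exact 95% confidence interval (CI) after each vaccine dose and overall". The second counts injections: "The percentage of doses followed by at least one local AE (solicited and unsolicited"), then general AEs and any AE, and each of these "will be tabulated, overall vaccination course, with exact 95% CI". The same computations are repeated for Grade 3, related and medically attended AEs, and a per-dose percentage is also planned for each solicited AE. No sentence says which injections count as doses.

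Section 3 states: "Formulation buffer will be administered in the 1D groups at Day 31 (Visit 3"). The 2D groups receive ChAd155-RSV at both visits. Under Section 11.5.4 all single-dose groups "will be pooled together as the pooled 1D RSV group". Table 2 shows the comparator groups receiving licensed vaccine at one of the two visits and buffer at the other, or buffer at both in placebo countries.

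The protocol's own vocabulary treats buffer as a dose. Table 15, which lists the study vaccines, has a column for number of doses that is filled in for buffer, with the footnote "The number of Formulation buffer doses depends on the study arm and study country". In the placebo schedule, Section 3 calls the Day 31 injection of the 1D RSV + Placebo group a dose.

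AEs are collected after both injections: "At each vaccination visit of the RSV investigational vaccine (Visit 1 [Day 1] and Visit 3 [Day 31]), a diary card will be provided" (Section 6.6.15), and the primary endpoint is "Occurrence of each solicited local and general AE, during a 7-day follow-up period after each vaccination" (Section 11.1).

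**The concern.** A percentage of doses invites the reader to treat it as a property of the injected product and to set 1D beside 2D. Here the two denominators differ in kind: 1D is one vaccine and one buffer injection per infant, 2D is two vaccine injections. If buffer causes fewer AEs than vaccine, the 1D figure is pulled down for a reason unrelated to the 1.5x10^10 vp dose, always in the same direction. The pooled comparator has the same problem, with a mix that depends on which countries recruit.

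The interval adds a second fault. An exact binomial CI on 100 doses assumes 100 independent observations, but they come from 50 infants with two injections each.

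Reactogenicity belongs to the primary objective, and the study rationale (Section 1.2.1) gives weight to comparing the single lower dose with the two higher doses.

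**Working it through.** **The protocol's own figures.** No per-dose rate or dose denominator is stated. The nearest figures, in Section 11.4, are per subject, and they reproduce:
- The maximum exact 95% CI width with n = 50 is 28.9 points (at 25/50); stated as under 30%.
- With 30% attrition, n = 35, it is 34.6 points (at 17/35); stated as up to 35%.
- The chance of at least one SAE at a 5% rate is 1 − 0.95^50 = 92.3%; stated as about 92%.

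These are sound but do not bear on the dose denominator.

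**Which injections are in the denominator.** Diary cards are issued at Visits 1 and 3, so solicited AEs relate to the Day 1 and Day 31 injections.

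| Group | Day 1 | Day 31 | Buffer share |
|---|---|---|---|
| 1D RSV | ChAd155-RSV | buffer | 1/2 |
| 2D RSV | ChAd155-RSV | ChAd155-RSV | 0 |
| Bexsero or Nimenrix alone | licensed vaccine | buffer | 1/2 |
| Synflorix or Menveo alone | buffer | licensed vaccine | 1/2 |
| Placebo | buffer | buffer | 1 |

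**Dilution.** Let p be the AE rate after 1.5x10^10 vp and q the rate after buffer. With 50 infants and both injections given:
- buffer counted: (50p + 50q)/100 = (p + q)/2
- only ChAd155-RSV counted: 50p/50 = p

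The protocol gives neither p nor q. Assuming p = 40% and q = 10%:
- 1D as planned: (20 + 5)/100 = 25%, exact 95% CI 16.9 to 34.7
- 1D, vaccine injections only: 20/50 = 40%, CI 26.4 to 54.8
- 2D with the same 40% per injection: 40/100 = 40%, nominal CI 30.3 to 50.3

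Two equally reactogenic dose levels would therefore appear 15 points apart. Over an assumed range, the 1D figure (and its ratio to p) is:

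| p | q = 2% | q = 10% | q = 20% |
|---|---|---|---|
| 20% | 11% (0.55) | 15% (0.75) | 20% (1.00) |
| 40% | 21% (0.53) | 25% (0.63) | 30% (0.75) |
| 60% | 31% (0.52) | 35% (0.58) | 40% (0.67) |

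The 1D figure is 52% to 100% of p, with no dilution when q = p.

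**Interval for 2D.** With two injections per infant and within-infant correlation ICC, the standard error is larger by sqrt(1 + ICC). For assumed ICC of 0.2, 0.4 and 0.6 the factor is 1.10, 1.18 and 1.26. The planned interval is too narrow by 1 − 1/factor, using unrounded factors: 9%, 15% and 21%. In the example the nominal width is 50.3 − 30.3 = 20 points; scaled by 1.10 to 1.26 it is about 22 to 25 points. The exact method is itself conservative, which offsets part of this.

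**The case against.** The strongest reply is that the undiluted comparison is already planned. The same paragraph gives percentages of subjects after each dose, for each study group as well as pooled, and repeats them for each solicited AE and for fever. Each visit in a study group has one product, so these tables already separate products: 1D after Dose 1 is 1.5x10^10 vp, 1D after Dose 2 is buffer, and both 2D columns are 5x10^10 vp. This stands, and it confines the problem. It does not repair the per-dose figure itself: splitting by study group leaves every 1D group and every active comparator group half buffer over the course.

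It can also be said that no sentence puts buffer in the denominator and that an analysis plan could define it. That is right: the reading is an inference. But the protocol's wording points one way. Holding rules 2a to 2c (Table 23) limit themselves to events after an investigational RSV vaccine, and Section 11.8.1 has no such limit.

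A third reply is that the per-dose figure describes the regimen as given. The overall percentage of subjects already does that, under a label that fits.

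A reader might infer more: that the lower dose will look milder throughout the safety results, or that safety decisions would be distorted. The documents do not support this. The holding rules count only events after RSV vaccine. The contrast in Section 11.8.2 uses percentages of subjects, RSV against comparator. No per-dose test of 1D against 2D is planned, and Section 11.11 calls comparative analyses exploratory. Subject-level CIs have one observation per infant and are unaffected.

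**Conclusion.** The point holds for the course-level per-dose tables only. On the plain reading, the 1D per-dose percentage is (p + q)/2, cannot be set beside the 2D figure, and is biased downward whenever buffer is less reactogenic than vaccine. The comparator figure is a country-dependent mix of products. The size rests on AE rates that the protocol does not give: 25% against 40% at p = 40% and q = 10%, and nothing if q = p. General symptoms that infants have anyway could bring q close to p, so the dilution may be small for some AEs.

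The per-dose exact CI is wrong as specified because it ignores pairing within infants. The shortfall for 2D is about 9% to 21% for assumed ICC 0.2 to 0.6, before allowing for the conservatism of the exact method.

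This is a correctable fault in a descriptive summary of a primary endpoint. It does not affect study conduct or any stated decision rule.

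**What to change.** Amend Section 11.8.1 to state that:
- per-dose percentages are tabulated by product injected: ChAd155-RSV 1.5x10^10 vp, ChAd155-RSV 5x10^10 vp, each licensed comparator, and formulation buffer, so that buffer is never combined with ChAd155-RSV;
- CIs for per-dose percentages allow for two injections per infant, or are omitted, with exact CIs kept for subject-level rates only;
- any descriptive comparison of the two dose levels is based on the percentage of subjects after Dose 1.

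The cost is a sentence or two, a few more table columns and a slightly wider CI where one is kept. No new data are needed, because Sections 6.2.2.2.1 and 6.2.2.2.2 already require the treatment number of every injection to be recorded.
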